Panel 2 Schedule of trial procedures: screening and initial treatment period (continued)

	Scree	ening ¹				I	nitial treat	ment perio	d			
Visit	11	2	3	4	5	6	7	8	9	10	112	12 ³
Week	-6	-2	0	2	4	6	8	10	12	14	15	16
Investigator assessments of efficacy (Section												
EASI	х		х	x	х	x	Х	Х	х	x		Х
SCORAD	х		х	х	х	х	Х	Х	х	х		Х
Subject assessments of efficacy (Section 10.	3.2)											
eDiary training		х										
eDiary completion9		<- ==										
POEM and DLQI			х	x	х	x	х		х			х
EQ-5D-5L and HADS			х		х		х		х			х
SF-36 and WPAI-GH			х				Х					Х
TSQM				x								х
Safety assessments (Sections 10.4 and 11)												
Vital signs	х		X ⁸	X ⁸	X ⁸	x	х	х	х	x		X ⁸
Physical examination	х		х				Х					Х
ECG	х		х				Х					Х
Serum pregnancy test	х											
Urine pregnancy test			х		х		х		х			х
Hepatitis B, C and HIV	х											
Serum chemistry, haematology, and IgE	X ¹⁰		х		х		х		х			Х
Urinalysis	Х		Х				х					Х

Trial ID: LP0162-1325	Date: 14-Aug-2018	Version: 4.0
		Page 20 of 169

Panel 2 Schedule of trial procedures: screening and initial treatment period (continued)

	Scree	ning ¹				Iı	nitial treat	ment perio	d			
Visit	11	2	3	4	5	6	7	8	9	10	112	12 ³
Week	-6	-2	0	2	4	6	8	10	12	14	15	16
Safety assessments (Sections 10.4 and 11)	afety assessments (Sections 10.4 and 11)											
Pharmacokinetics				Х	Х					х	X ²	х
ADA			Х		Х							х
Adverse events	х	х	х	х	х	х	х	х	х	х		х
Other assessments (Section 10.5)												
Skin swabs (S. aureus)			Х									х
Skin swabs (microbiome) ¹¹			х				х					х
Serum biomarkers (small panel)			х		Х		х					х
Serum biomarkers (large panel) ¹¹			х		х		х					х
Skin biopsies ¹¹			X ¹²		х							х
Photography ¹¹			х	х	х	х	х	х	х	х		Х

 For subjects who do not require a wash-out, visits 1 and 2 will be combined and screening will be reduced to 2 weeks; hence, these subjects will only attend visit 2 (Week -2) which will include all assessments shown under Week -6. Similarly, for subjects who only require a 2-week wash-out, screening visits 1 and 2 will be combined (Week -2). The screening period has a maximum duration of 6 weeks.

2) At Week 15, subjects will only have a blood sample drawn. No assessments that require trial personnel will be performed. Collection of AEs and reporting of concomitant medication and procedures will occur at the following trial visit.

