10.4.5 Laboratory testing

The following safety samples will be analysed by a central laboratory: chemistry, haematology, serology, and serum pregnancy (Panel 13). Urine samples will be tested at the trial site with a dipstick; if abnormal, a urine sample will be sent to the central laboratory for further analysis.

A laboratory manual will be provided to the sites that specifies the procedures for collection, processing, storage, and shipment of samples, as well as laboratory contact information specific to this trial.

Samples for laboratory testing will be collected according to the SoP (Section 4).

Panel 13 Central laboratory testing	Panel 13	Central	laboratory	testing
-------------------------------------	----------	---------	------------	---------

Chemistry	Haematology
Sodium	Erythrocytes
Potassium	Hematocrit
Creatinine	Hemoglobin
Urea nitrogen	Erythrocyte mean corpuscular volume
Calcium	Erythrocyte mean corpuscular haemoglobin
Alkaline phosphatase	concentration
Aspartate aminotransferase	Leukocytes
Alanine aminotransferase	Neutrophils, neutrophils/total cells
Gamma glutamyl transferase	Lymphocytes, lymphocytes/total cells
Bilirubin ¹	Monocytes, monocytes/total cells
Lactate dehydrogenase	Eosinophils, eosinophils/total cells
Cholesterol	Basophils, basophils/total cells
LDL cholesterol	Thrombocytes
HDL cholesterol	Serology
Triglycerides	Hepatitis B virus surface antigen ⁴
Glucose (non-fasting)	Hepatitis B virus surface antibody ⁴
Albumin	Hepatitis B virus core antibody ⁴
Protein	Hepatitis C virus antibody ⁴
Tryptase ²	HIV-1 antibody ⁴
	HIV-2 antibody ⁴
	Immunoglobulin E ⁵
Urinalysis ³	Serum pregnancy test (females only) ⁴
Protein	Choriogonadotropin beta
Glucose	
Ketones	
Occult blood	
Leukocytes	
Nitrite	

1) If bilirubin is above upper limit of normal, direct and indirect bilirubin will also be measured.

2) Only measured in case of suspected anaphylaxis (Section 9.2).

 Urine samples will be tested at the trial site (dipstick). In case of abnormal dipstick results, a urine sample will be sent to the central laboratory for microscopic examination (leukocytes, erythrocytes, and casts).

Measured at screening only.

5) Not measured at screening.

HDL, high density lipoprotein; LDL, low density lipoprotein.

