12.3.7 Analysis of safety

The analyses of safety will be based on the safety analysis sets. The reporting of safety data will be presented separately for the initial treatment, the maintenance treatment, and the open-label treatment.

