12.3.7.3 Clinical laboratory evaluation

The change in each of the laboratory parameters from baseline to each visit will be summarised by visit and treatment group as mean, standard deviation, median, minimum and maximum values for the safety analysis set, the maintenance safety analysis set, and the open-label safety analysis set.

Laboratory parameters will be classified as 'low', 'normal' or 'high', depending on whether the value is below, within or above the reference range, respectively. A shift table will be produced showing the categories at baseline against those at end of treatment. Subjects with laboratory parameters outside the reference range will be listed.

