# 6.7.4 Laboratory Data

Laboratory data will be summarised and listed.

For the laboratory values, if the value is below the lower limit of quantification, half of the lower limit will be used for quantitative summaries. If the value if above the upper limit of quantification, the upper limit value will be used.

If more than one laboratory value is reported for the same visit, the latest value will be used in summary statistics and analyses.

Potentially clinically significant values will be defined as displayed in Table 2.

Protocol Lab parameter	SI Unit	PCS low	PCS High
Biochemistry			
Sodium	mmol/L	< 129 mmol/L, < 125 mmol/L	> 160 mmol/L
Potassium	mmol/L	< 3 mmol/L, < 2.5 mmol/L	> 6.5 mmol/L, > 7.5 mmol/L

Table 2: Potentially clinically significant biochemistry and haematology values

Trial ID: LP0162-1325	Date: 20-May-2019	Version: 1.0
		Page 24 of 31

Creatinine	umol/L	N/A	> 1.5 xULN, > 3 xULN
Calcium	mmol/L	< 1.9 mmol/L	> 3.0 mmol/L,
			> 3.5 mmol/L
Alkaline phosphatase	U/L	N/A	> 3xULN
Aspartate	U/L	N/A	> 3xULN, $> 5$ xULN,
aminotransferase			> 10 xULN, > 20 xULN
Alanine aminotransferase	U/L	N/A	> 3xULN, $> 5$ xULN,
			> 10 xULN, > 20 xULN
Bilirubin	umol/L	N/A	>2xULN
Cholesterol	mmol/L	N/A	> 6.2 mmol/L
LDL cholesterol	mmol/L	N/A	> 4.1 mmol/L,
			> 4.9 mmol/L
HDL cholesterol	mmol/L	N/A	> 1.6 mmol/L
Triglycerides	mmol/L	N/A	> 2.3 mmol/L,
			> 5.6 mmol/L
Glucose (non-fasting)	mmol/L	< 3.9 mmol/L	>11.1 mmol/L
Haematology			
Haemoglobin	g/L	<110 g/L, < 80 g/L	> 185 g/L for male,
-	-		> 165 g/L for female
Neutrophils, absolute	10  /L	$< 1.5 \ 10^{9}/L, < 1.0 \ 10^{9}/L,$	N/A
count		< 0.5 10  /L	
Lymphocytes, absolute	$10^{9}/L$	$< 1.0 \text{ x } 10^9 / \text{L},$	$> 5.0 \text{ x } 10^9/\text{L}$
count		$< 0.5 \text{ x } 10^9/\text{L}$	
Monocytes, absolute count	$10^{9}/L$	$< 0.1 \text{ x } 10^9/\text{L}$	$> 0.8 \text{ x } 10^9/\text{L}$
Eosinophils, absolute	$10^{9}/L$	N/A	> 1.5, > 5.0
count			
Basophils, absolute count	$10^{9}/L$	N/A	> 0.2
Thrombocytes	10  /L	$< 100 \text{ x } 10^9 \text{/L},$	$>450 \text{ x } 10^9/\text{L}$
-		$< 30 \text{ x } 10^9/\text{L},$	
	• • • • •	$< 10 \times 10^{9}/L$	1

PCS: potentially clinically significant; ULN: Upper limit of normal, i.e. upper limit of normal reference range.

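### No planned laboratory table counts subjects whose value went low or high during treatment and was back in range by its end

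*Protocol*

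**What the plan says.** Protocol section 12.3.7.3 plans three laboratory outputs.

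- A continuous summary: "The change in each of the laboratory parameters from baseline to each visit will be summarised by visit and treatment group", giving mean, standard deviation, median, minimum and maximum.
- A categorical table based on the reference range: "A shift table will be produced showing the categories at baseline against those at end of treatment".
- A listing: "Subjects with laboratory parameters outside the reference range will be listed".

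Section 12.3.7 adds that "The reporting of safety data will be presented separately for the initial treatment, the maintenance treatment, and the open-label treatment". Neither section says which sample counts as end of treatment in each period.

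SAP section 6.7.4 states that "Laboratory data will be summarised and listed" and that "Potentially clinically significant values will be defined as displayed in Table 2". It does not name a table in which PCS values are counted, or the time window over which they would be counted.

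**The concern.** A shift table gives a count of subjects per arm who changed category, judged against a fixed range and independent of the investigator's opinion. Tied to the last sample alone, it shows who was out of range at the end, not who went out of range while on drug. A laboratory effect that comes early and settles, or that resolves after dosing is interrupted, would leave little trace in it.

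The other outputs do not supply the missing count. A mean or median dilutes a change that affects few subjects. A minimum or maximum is one extreme change per arm and visit, and does not show whether a range limit was crossed. A listing gives no rate and no comparison between arms. What is at stake is how readily a transient safety signal can be seen, not any confirmatory conclusion.

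**Working it through.** The plan gives no figure on this point to reproduce. The check is a count of samples and parameters, followed by one illustration.

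**1. Samples taken.** In the schedules of Protocol section 4, the row "Serum chemistry, haematology, and IgE" is marked at baseline and at Weeks 4, 8, 12 and 16 (Panel 2), which is 4 post-baseline samples. Panel 3 marks Weeks 20 to 52 every 4 weeks: (52 − 20)/4 + 1 = 9 samples. The total to Week 52 is 4 + 9 = 13.

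**2. Samples used by the shift table.** Made per period, it uses 1 of 4 in the initial period (3 skipped) and 1 of 9 in maintenance (8 skipped). Made once at Week 52, it uses 1 of 13 (12 skipped).

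**3. Where a transient abnormality at a scheduled visit can appear.**

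- By-visit change summary: yes, for every parameter, but as a continuous value.
- Listing of out-of-range subjects: yes, and the listing is not restricted to the last visit.
- AE tables: yes, if the investigator judges it clinically significant. Protocol Appendix 2 makes such a finding an AE, and section 12.3.7.1 tabulates treatment-emergent AEs by treatment group.
- End-of-treatment shift table: no.
- PCS table: none is committed to.

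Two handling rules also favour later values. Under SAP section 6.7.4, the latest of several results at one visit is used in summaries. Protocol section 10.4.5 requires clinically significant abnormal tests to be repeated, so a normal retest recorded under the same visit replaces the abnormal result. Under SAP section 6.8.6, unscheduled data enter by-visit summaries only when the scheduled visit has none.

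**4. Coverage of the PCS limits.** Panel 13 (Protocol section 10.4.5) lists 19 chemistry and 12 haematology parameters, counting each differential cell type once: 19 + 12 = 31. SAP Table 2 gives limits for 13 + 7 = 20, leaving 31 − 20 = 11 without: urea nitrogen, GGT ("Gamma glutamyl transferase" in the panel), lactate dehydrogenase, albumin, protein, tryptase, erythrocytes, haematocrit, mean corpuscular volume, mean corpuscular haemoglobin concentration and leukocytes. Tryptase is measured only in suspected anaphylaxis, so 10 of the 11 are measured on schedule.

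Of the 20 limits, 12 run in one direction only:

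- 9 in chemistry: creatinine, alkaline phosphatase, AST, ALT, bilirubin, cholesterol, LDL, HDL and triglycerides.
- 3 in haematology: neutrophils, eosinophils and basophils.

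Neutrophils have only a low limit and total leukocytes have none, so a transient high count of either has no threshold at all. Some limits also sit well outside the reference range: for ALT the first is above 3 times the upper limit of normal.

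**5. Illustration.** Assume the shift is made per period with the last of n scheduled samples, and that an abnormality is present at k of the n samples, placed at random. Then P(missed) = 1 − k/n.

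- Initial period, k = 1, n = 4: 1 − 1/4 = 3/4.
- Maintenance, k = 1, n = 9: 1 − 1/9 = 8/9.
- Initial period, k = 2, n = 4: 1 − 2/4 = 1/2.
- An abnormality that lasts to the final sample: 0.

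**The case against.** The strongest reply is that transient abnormalities are reported already. Every scheduled value enters a by-visit summary with its extremes, every out-of-range subject is listed, and anything judged clinically significant is tabulated as an AE. This stands against a stronger claim that a reader might make, namely that such abnormalities are never tabulated. It does not supply a count of subjects out of range at any time.

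A reader might also infer that the gap is confined to parameters without a PCS limit, and that Table 2 covers the rest. The documents do not support this: the SAP defines limits without committing to an output, and 12 of the 20 are one-sided.

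A third inference is that subjects who stop dosing because of an abnormality would be hidden by a normalised last value. The documents do not show this. The specific laboratory criteria for permanent discontinuation in Protocol section 9.8.1 concern ALT, AST and bilirubin. Subjects who stop are asked to attend an early termination visit, whose assessments include laboratory samples, and AEs leading to withdrawal from the trial are tabulated and listed.

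Finally, worst-value tables gather chance excursions. Assuming a 95% reference range and independent samples, a subject with no true change is out of range at least once with probability 1 − 0.95^4 = 19% over four samples and 1 − 0.95^9 = 37% over nine, against 5% at one sample. Correlation within subject lowers the first two figures. This cost is real. It falls on all arms, and both the initial and the maintenance period have a randomised placebo arm for comparison. Baseline against end of treatment remains a legitimate display, and some parameters without a limit overlap with others that have one (haematocrit with haemoglobin, for example). These are reasons to keep the present table and to rate the point as minor.

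**Conclusion.** The point holds in a limited form. Reference-range categories are tabulated only at baseline against end of treatment, and neither document commits to a count of subjects who were low or high at any time on treatment.

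The figures of 3/4 and 8/9 are not estimates of what this trial would miss. They rest on an abnormality at exactly one randomly placed scheduled sample and on a shift made per period. The documents give no data on the duration of abnormalities, and longer ones are missed less often.

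The per-period reading is itself an assumption. Section 12.3.7 points to it, but section 12.3.7.3 does not define end of treatment by period. A reader might infer a single shift at Week 52, which would mix open-label tralokinumab into the placebo group. The text does not settle this, so it needs a definition and not a presumption of error.

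This is a minor improvement to safety reporting. Sample size, power, alpha and the efficacy analyses are unaffected.

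**What to change.** In SAP section 6.7.4, for each treatment period and by treatment group, add a shift from baseline to the lowest and to the highest on-treatment value. Use scheduled and unscheduled samples, and include all Panel 13 chemistry and haematology parameters measured on schedule. Keep the end-of-treatment shift as a second table, and define end of treatment for each period.

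The cost is one more standard table per period, with no new data. Out-of-range percentages will rise in all arms through chance excursions, so the table should be read as a comparison between arms: tralokinumab against placebo in the initial period, and Q2W, Q4W and placebo in maintenance. Subjects can transfer from maintenance to open-label treatment from Week 22 (Protocol section 7.1), so the number of samples per subject may differ between arms. Showing that number beside the maintenance counts would keep the comparison fair. The open-label table has no control arm and is descriptive only.

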12.3.7.4 Pharmacokinetics

All the PK samples in the trial are trough samples apart from the Week 15 sample. Area under the curve (AUC) will be calculated for subjects where all the 3 samples planned at Week 14, 15 and 16 have measurable concentrations. The C_{trough} concentration and the calculated AUC will be listed by treatment group and descriptive statistics will be provided.

 C_{trough} and AUC values from subjects with positive ADA/nAb will be compared to values from subject with negative ADA/nAb if data permits.

The PK data will be merged with those from other clinical trials with tralokinumab for a population-based meta-analysis. Results of the meta-analysis will be presented in a separate pharmacometrics report outside of the CTR.

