1.3 Acknowledgement statement investigator(s)

Each participating investigator must agree to the approved clinical trial protocol and consolidated clinical trial protocol(s) comprising any subsequent amendment(s) by signing a Clinical Trial Protocol Acknowledgement Form or a similar document.

Trial ID: LP0162-1325	Date: 14-Aug-2018	Version: 4.0
		Page 3 of 169

Protocol amendment summary of changes table

Document history	Date	Type of amendment
Amendment 3 (substantial)	14-Aug-2018	Global
Amendment 2 (substantial)	12-Dec-2017	Global
Amendment 1 (substantial)	28-Aug-2017	Global
Original protocol	03-Mar-2017	

Amendment 3 (14-Aug-2018)

This amendment is considered to be substantial based on the criteria set forth in Article 10(a) of Directive 2001/20/EC of the European Parliament and the Council of the European Union (33).

Overall rationale for the amendment

The main reason for the amendment is that a new anti-drug antibody (ADA) assay has been developed with improved tralokinumab tolerance. This means that the presence or absence of ADA can be determined in serum samples with tralokinumab present. Previously, this was not possible and therefore ADA sampling at the end of the 14-week off-treatment safety follow-up was originally required for the ADA evaluation. Thus, the new ADA assay will allow eligible subjects who have completed the treatment periods of trial LP0162-1325 to continue into the long-term extension trial (conducted under a separate protocol [LP0162-1337, ECZTEND]) without completing the safety follow-up period in the present trial. These subjects will have their safety follow-up period after end-of-treatment in the long-term extension trial.

In addition, the amendment includes other changes, as presented in the table below.

Note: The table below describes the changes in each section. Changes have either been summarised (written with plain text only) or marked as tracked changes (text added to the protocol is written in **bold** and deleted text has a line through it).

Trial ID: LP0162-1325

Section number and name	Description of change	Brief rationale

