## 6.7.7 Pharmacokinetics and anti-drug antibodies

Pharmacokinetics and anti-drug antibodies data will be summarised and listed.

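### AUC is calculated only when all three samples are measurable and is then compared by ADA/nAb status, so any antibody-positive subject with a non-measurable sample drops out of the AUC half of that comparison

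*Protocol*

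**What the plan says.** Protocol 12.3.7.4 (Pharmacokinetics) makes four statements that matter here.

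- On sample type: "All the PK samples in the trial are trough samples apart from the Week 15 sample".
- On who gets an AUC: it "will be calculated for subjects where all the 3 samples planned at Week 14, 15 and 16 have measurable concentrations".
- On the antibody comparison, for C_trough and AUC alike: "values from subjects with positive ADA/nAb will be compared to values from subject with negative ADA/nAb if data permits".
- On later use: "The PK data will be merged with those from other clinical trials with tralokinumab for a population-based meta-analysis". That work is reported separately from the trial report.

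The SAP adds one line on this topic, in section 6.7.7: "Pharmacokinetics and anti-drug antibodies data will be summarised and listed". It has a rule for low values, "if the value is below the lower limit of quantification, half of the lower limit will be used for quantitative summaries", but this stands in section 6.7.4 (Laboratory Data) and is not extended to drug concentrations.

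**The concern.** The comparison asks whether antibodies lower exposure. A subject whose antibodies lower exposure far enough to make even one of the three samples non-measurable has no AUC and cannot contribute to the AUC answer. The subjects with the largest loss of exposure are the ones most likely to be missing, and those who remain look more like the antibody-negative group.

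At stake is the reading of one immunogenicity result. A reader could take similar AUCs in the two groups as reassurance when part of the similarity comes from the entry rule. The protocol treats the frequency of ADA as an additional secondary endpoint. Amendment 3 was prompted mainly by an assay with which "the presence or absence of ADA can be determined in serum samples with tralokinumab present". Antibody-positive subjects can therefore be classified whether or not drug is measurable, and the AUC rule uses only those with drug measurable at all three samples.

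**Working it through.** The plan gives no figure on this point, so there is nothing to reproduce. The check is textual, followed by an illustration of direction.

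**1. Does any other text repair the rule?**

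- SAP 6.7.7 sets no rule for non-measurable concentrations.
- SAP 6.8.7 refers missing values back to the protocol. Protocol 12.3.11 refers them to the sections on the individual analyses. For PK, that is 12.3.7.4 itself.
- The half-limit rule is in the SAP's laboratory section. The protocol keeps laboratory testing (10.4.5) apart from PK (10.4.6), and Panel 13, the list of central laboratory tests, does not include tralokinumab concentration. The rule cannot be assumed to cover PK.
- The population meta-analysis is reported elsewhere, and its handling of low values is not described.

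Nothing repairs the rule for AUC.

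**2. Does the rule also reach C_trough?** No. The measurability condition is attached to AUC only. How a non-measurable trough enters (as zero, as half the limit, or as missing) is left open. If it were treated as missing, the same selection would arise there.

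**3. Direction, with assumed inputs.** Let c be the share of ADA-positive subjects with at least one non-measurable sample. Let L be their AUC relative to ADA-negative subjects, and r the relative AUC of the other ADA-positive subjects. No ADA-negative subject is assumed to be lost. None of these values is in the documents.

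- Ratio under the written rule: r.
- Arithmetic-mean ratio with everyone kept: (1 − c) × r + c × L.

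| r | c | Written rule | Everyone kept, L = 0.01 | Everyone kept, L = 0.05 |
|---|---|---|---|---|
| 1.0 | 0% | 1.00 | 1.00 | 1.00 |
| 1.0 | 10% | 1.00 | 0.9 + 0.001 = 0.901 | 0.9 + 0.005 = 0.905 |
| 1.0 | 30% | 1.00 | 0.7 + 0.003 = 0.703 | 0.7 + 0.015 = 0.715 |
| 0.7 | 10% | 0.70 | 0.63 + 0.001 = 0.631 | 0.63 + 0.005 = 0.635 |
| 0.7 | 30% | 0.70 | 0.49 + 0.003 = 0.493 | 0.49 + 0.015 = 0.505 |

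**4. A milder pattern.** One low sample is enough to lose the AUC, and Week 15 falls mid-interval, so it may be measurable when the troughs are not. Assume, in arbitrary units, troughs substituted at 0.5, Week 15 at 40, and ADA-negative subjects flat at 80.

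- Trapezoid AUC over the two weeks: (0.5 + 40)/2 + (40 + 0.5)/2 = 40.5, against 80 × 2 = 160. So L = 40.5/160 = 0.253.
- With r = 1 and c = 10%: 0.9 + 0.1 × 0.253 = 0.925.
- With r = 1 and c = 30%: 0.7 + 0.3 × 0.253 = 0.776.

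The direction is the same in every case with c above zero. The size depends wholly on c, L and r.

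**The case against.** The strongest reply is that AUC is only half of the planned comparison. C_trough is compared in the same sentence, without the condition, and every sample but Week 15 is a trough. A reader might infer from the AUC rule that subjects who clear the drug disappear from the search for antibody effects altogether. The documents do not support that, because no written rule removes them from the C_trough comparison. This part of the reply stands and sets the scope of the point.

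Four further arguments deserve weight.

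- Subjects with faster clearance but measurable drug keep their AUC and still lower the ratio. This is correct: only those with a non-measurable sample are lost.
- Such subjects may be rare or absent. The protocol equates 16 weeks with 5 half-lives (inclusion criterion 11, exclusion criterion 29), which is 16/5 = 3.2 weeks each. With dosing every 2 weeks, non-measurable drug at Weeks 14 to 16 would need a very large clearance effect. This is a fair argument about likelihood, but it does not justify the rule if such subjects occur.
- Other outputs bear on immunogenicity. Protocol 12.3.7.5 lists IGA and EASI change for subjects who develop ADA, and allows associations of ADA with adverse events to be evaluated. These lessen the consequence without correcting the AUC result.
- Requiring measurable samples for a three-point AUC is defensible, and half the limit is an arbitrary value. This stands as a reason to keep the measurable-only AUC and show the substituted version beside it.

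**Conclusion.** The point holds for AUC and is minor. The entry rule depends on the outcome, and no other text corrects it. It moves the AUC ratio towards no difference if ADA/nAb-positive subjects with a non-measurable sample exist, if their exposure is lower than that of the positive subjects who remain, and if negative subjects are not lost in a way that offsets this.

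The size cannot be derived. The documents give no ADA rate, no assay limit and no share of non-measurable samples, and they leave assay details to a bioanalytical report. If nobody is affected, the bias is zero. The ratios in the working show direction under assumed inputs. A reader might take them as an estimate for this trial, but nothing in the documents supports that use.

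A reader might also infer that an efficacy conclusion or the type I error rate is at risk. Neither is. The comparison is made only if data permit, has no test specified, and lies outside the testing hierarchies of Protocol 12.3.4 and SAP 6.6.1.

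**What to change.** Add to SAP 6.7.7, for the ADA/nAb comparison only:

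- In tralokinumab-treated subjects who were still being dosed through Week 14 and who have all three samples taken, calculate AUC with below-quantification concentrations set to half the limit, which is the SAP's own laboratory rule. The restriction keeps out placebo subjects and those whose concentrations are low because dosing stopped.
- Apply the same substitution to C_trough.
- Show this AUC beside the measurable-only AUC.
- Report, by ADA/nAb status, the number of subjects without a measurable-only AUC, separating non-measurable from missing samples. These counts alone tell the reader whether any selection took place.

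The cost is a few sentences and a small programming change. The downside is that a few AUC values rest on a substituted concentration. On the arithmetic scale of Protocol 12.3.10 (mean, median, standard deviation, range), the mean hardly depends on the value chosen: with r = 1 and c = 10%, the mean ratio is 0.901 or 0.905 for L of 0.01 or 0.05. A geometric mean would be far more sensitive (0.63 or 0.74 for the same inputs), so the substituted AUC should be summarised on the arithmetic scale.
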